2. CLINICAL STUDY BACKGROUND

2.1 Piroxicam Plus Counterirritant gel

In 1972, an innovator topical analgesic product was introduced to the Indonesian market. Counterpain® is one of the topical analgesic products that is known not only in Indonesia, but also in other Southeast Asian countries such as Malaysia, Philippines, and Thailand. Counterpain® as an innovator product in Indonesia has several variants, namely Counterpain® cream helps with a warm sensation that relieve muscle pain, Counterpain® Cool with a cool sensation can be used for cooling during exercise and Counterpain® PXM effectively relieves inflammation in musculoskeletal and joint.

There are many topical preparations containing non-steroidal anti-inflammatory drugs, namely diclofenac, ketoprofen and also piroxicam. Piroxicam preparations that are registered as innovator products in Indonesia :

- Feldene® gel which only contains Piroxicam as an active substance and
- Counterpain® PXM which contains Piroxicam, and Counterirritant: methyl salicylate, menthol and eugenol as active substances.

Counterpain® PXM was first registered and obtained marketing authorization in Indonesia in 2004 by Bristol Myers Squibb (BMS). The registration process was completed by providing research data of Counterpain PXM-Thailand clinical study in 1995 as supporting data.

The pharmacokinetic parameters of piroxicam 0.5% topical gel were taken from data were determined in 20 healthy volunteers (6 women and 14 men) following application of multiple doses (20 mg piroxicam daily) over 14 days. 21 blood samples were drawn from each patient beginning just before application of the first dose, with the final sample taken 14 days after application of the last dose. Plasma concentrations of piroxicam were determined by high-performance liquid chromatography using UV detection at 340nm. There was considerable interindividual variation in piroxicam half-lives with a mean of 79 hours. Mean piroxicam plasma concentrations at steady-state were between 300 and 400 ng/ml, which is about 5% of those observed after equivalent doses of oral or intramuscular piroxicam. No adverse experiences were reported during the study period. Thus, the results of this study confirm the minimal systemic absorption of piroxicam during multiple-dose application of the 0.5% topical gel and the excellent tolerability of this mode of piroxicam therapy.

A study that conducted in 1995, with its title “The study of efficacy and safety of anti inflammatory and analgesic cream in the treatment of musculoskeletal pain” described that the standard piroxicam gel 0.5 % versus the test drug, piroxicam and analgesic cream containing methylsalicylate, eugenol and menthol are equally effective and well tolerated in the treatment of musculoskeletal pain. It was interesting to note that most of patients prefer to have the warm feeling after application as it indicates that the medication was working.

Another study that conducted in 1995, with its title “A double-blind randomized study to evaluate the safety and effectiveness of 0.5% Piroxicam gel compared to Counterpain Plus (combination of 0.5% piroxicam gel, 10% methyl salicylate, 5.4% menthol and 1.36% eugenol) in patients with mild osteoarthritis. As conclusion that both Counterpain Plus and Piroxicam gel are equally effective in gradual relief of the knee joint pain that assessed by Visual Analog Scale or Verbal Rating Scale. Both also equally effective help restore the patient’s functional ability.

The last study that executed in 1995 with its title “Comparative study of the clinical effects of Counterpain Plus and Feldene Gel on knee arthrosis”, found that there was no difference between the terms of biographic data, stage of degeneration, Moberg’s functional scores and severity of pain between the groups at pre-trial and the end of the study. Counterpain Plus and Feldene gel have comparable clinical effects on the treatment of knee arthrosis.

In 2009, Taisho Pharmaceutical Holdings acquired the commercial rights of Counterpain in Indonesia. The distribution permit for the Counterpain® PXM product was transferred to PT Taisho Pharmaceutical Indonesia thereafter. Counterpain® PXM as a topical non-steroid anti inflammation drugs (NSAID) Plus Counterirritant such as methyl salicylate, eugenol and menthol, can be used to help relieve musculoskeletal pain and inflammation such as osteoarthritis, acute post-traumatic disorders: tendinitis, tenosynovitis, periarthritis, strain, sprain, muscle tense and low back pain, this indication is approved by BPOM RI in 2011.

There are no recent clinical studies in 2000 onwards that examine the efficacy of Piroxicam plus Counterirritant gel in the treatment of musculoskeletal pain compare with others topical NSAIDs such as Diclofenac gel or Ketoprofen gel.

2.2 Justification to conduct clinical study

Acute musculoskeletal pain describes conditions like a sprained ankle or a muscle pull. These usually get better over two or three weeks without treatment, but can be very painful while they

last. Topical non-steroidal anti-inflammatory drugs (NSAIDs) are applied to unbroken skin where it hurts as gels, creams, sprays, or plasters. Topical NSAIDs penetrate the skin, enter tissues or joints, and reduce processes causing pain in the tissue. Drug levels in the blood with topical NSAIDs are very much lower than with the same drug taken by mouth. This minimises the risk of harmful effects.

The review from Cochrane in 2019, “Topical NSAIDs for acute musculoskeletal pain in adults”, formulations of topical diclofenac, ibuprofen, ketoprofen, piroxicam, and indomethacin demonstrated significantly higher rates of clinical success (more participants with at least 50% pain relief) than matching topical placebo (moderate or high quality data). From the 42 clinical studies data that taken into the systematic reviews, 15 studies are discussed about Diclofenac, and only 3 studies discussed about efficacy of Piroxicam gel in musculoskeletal pain. None of those data explained about Piroxicam gel plus Counterirritant.

Another review from Global Pain Faculty “The burden of musculoskeletal pain and the role of topical non-steroidal anti-inflammatory drugs (NSAIDs) in its treatment. Ten underpinning statements from a global pain faculty”, published on Current Medical Research and Opinion, 2021, presents the conclusions of a detailed discussion on the role of topical NSAIDs during a round table Global Pain Faculty meeting held in Amsterdam in 2019 and subsequent discussions online. The document considers the place of topical therapies alongside other pharmacological and non-pharmacological treatments and presents the evidence for the benefits and harms of topical NSAIDs including indicators of efficacy for three main topical NSAIDs– diclofenac, ibuprofen and ketoprofen – based on almost 15,000 participants in randomized controlled trials for acute and chronic musculoskeletal pain. Randomized controlled trial evidence suggests that adverse events for active topical NSAIDs are similar to placebo. In this review, there is no discussion about effectiveness of Piroxicam gel especially Piroxicam gel plus Counterirritant in musculoskeletal pain.

A study that published in 2018, with its title “Relative efficacy and safety of topical non-steroidal anti-inflammatory drugs for osteoarthritis: a systematic review and network meta-analysis of randomised controlled trials and observational studies”, showed that systematic review and network meta-analysis of RCTs and observational studies and have ranked the topical NSAIDs (including salicylate) based on the results. Among all available topical NSAIDs, diclofenac patches were most effective for pain relief and piroxicam gel was the best option to improve function.

By referring to above data from comprehensive review studies and meta-analyses studies, it can be seen that diclofenac gel has more clinical studies data compared to piroxicam gel, so the use of diclofenac gel for the treatment of musculoskeletal pain can be traced with the support of an adequate clinical data whereas this data becomes the basis for selecting standard topical drugs for musculoskeletal pain.

For this reason, a clinical study will be conducted to compare the effectiveness of Piroxicam plus Counterirritant gel with others topical Non Steroid Anti Inflammation Drugs such as Piroxicam gel and Diclofenac gel in the adult population with musculoskeletal pain. This clinical data will be used as a standard treatment in management of musculoskeletal pain.

The clinical study will be conducted with the concept of Investigator Initiated Trial (IIT) with the purpose to developing education and health standards in Indonesia, the result of study will be the source to develop a standard guidance in management of musculoskeletal pain using

topical non steroid anti inflammation drugs especially in Eminence and general in all sports medicine clinic in Indonesia.

3. COMPLIANCE WITH GCP

This study will be conducted in accordance with Good Clinical Practice (GCP), as defined by the International Conference on Harmonization (ICH) and in accordance with Indonesian National Agency for Drug and Food Control Guidance (Pedoman Cara Uji Klinik yang Baik - CUKB). The principal investigator shall conduct this study after agreeing with the sponsor on the content of the protocol of this study and the case report form and compliance with them.

4. STUDY OBJECTIVES

The objectives of this study is to demonstrate the equivalency of efficacy and safety in reducing musculoskeletal pain between Piroxicam plus Counterirritant gel versus Piroxicam gel and Diclofenac gel, applied for 6 ± 1 days in Indonesian population.

Justification:

Piroxicam plus Counterirritant, Piroxicam, Diclofenac are considered as topical Non-Steroid Anti Inflammatory Drugs (NSAIDs). Diclofenac more common to use as a standard topical treatment since they have more clinical studies data than others topical NSAIDs. To demonstrate that Piroxicam plus Counterirritant has the same efficacy with Piroxicam, Diclofenac, the dedicated clinical study need to be conducted.

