The selection of difference more than equal to 3 was chosen because if the participant has moderate pain at the beginning of the treatment, then at the end of the treatment there is a decrease in pain to mild pain. This can be seen that the treatment is effective in dealing with musculoskeletal pain.

5.2 Secondary End-Point:

- 1) In data related to safety assessment, the number of participants who experienced adverse events (including serious adverse events) with each symptom present will be recorded and causality of adverse events and serious adverse events assessed with the help of Naranjo's algorithm

Justification:

At the 1st visit, participants will bring home Participant's Diary. Participants need to fill in if they experienced with others symptoms after get the treatment. Also they need to file the rescue medication that they consume during the study timeline. On the 2nd visit and last visit the Investigator will ask about the diary and confirmed the symptoms and medication. When there is safety report, the Investigator will fill in the Safety Form from BPOM RI (Form Kuning MESO) and assess the safety events with the help of Naranjo's algorithm.

The type of symptoms and the number of participants who have symptoms and including side effects will be recorded and become data related to product safety.

- 2) Investigator Assessment on Participants motions, through Range of Motion (ROM) and Muscle test.

Justification:

One of the symptoms that must be assessed when there is musculoskeletal pain is the range of motion and muscle movement to perform an activity. Therefore, an assessment for the examination of the range of motion and muscle strength carried out by the examining doctor is needed to determine the effect of the treatment carried out in the success of performing the activity.

The effectiveness of the treatment will be seen from the progress in the range of motion that can be performed by the participant at the end of the treatment compared to the beginning of the treatment according to scientific standards.

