6.7 Sample Size

Assumptions

- Outcome	: Pain score
- Standard deviation (σ)	: 1.81
- Clinically meaningful margin (Δ or δ)	: 1.0
- Power	: 80% ($Z_{1-\beta} = 0.84$)
- Significance level (α)	: 0.05

Reference standard deviation from Kocak AO, Dogruyol S, Akbas I, Menekse TS, Gur STA, Kocak MB, Cekmen B, Orun S, Cakir Z. Comparison of topical capsaicin and topical piroxicam in the treatment of acute trauma-induced pain: A randomized double-blind trial. Am J Emerg Med. 2020 Sep;38(9):1767-1771. doi: 10.1016/j.ajem.2020.05.104. Epub 2020 Jun 2. PMID: 32739846.

For **equivalence trials with 3 groups**, you typically plan for **pairwise equivalence testing**:

- Diclofenac vs. Piroxicam
- Diclofenac vs. PXM plus Counterirritant
- Piroxicam vs. PXM plus Counterirritant

This means you must **adjust α** to account for **multiple comparisons**, commonly using **Bonferroni correction**:

$$\text{Adjusted } \alpha = 0.05 / 3 = 0.0167 \rightarrow Z_{1-\alpha/2} \approx \mathbf{2.39}$$

Sample Size Formula and Calculation

Using the formula for equivalence trials:

$$n = ((Z_{1-\alpha/2} + Z_{1-\beta}) \times \sigma / \Delta)^2$$

Substituting the values:

$$n = ((2.39 + 0.84) \times 1.81 / 1.0)^2$$

$$n = (4.059 \times 1.81)^2 = (7.35)^2 = 54.0$$

Sample size per group (rounded): 54

Total sample size for 3 groups: 162

With 10% dropout:

Total = $162 / (1 - 0.10) \approx 180$ participants

Recommended: 60 participants per group

The clinical study will be recruited in total 180 subjects, which means 60 subjects per arm.

Justification:

- We used the reference from Kocak et al. because: The study used topical piroxicam, which is the main active ingredient in Counterpain PXM. The study was randomized, double-blind, and controlled, and reported the standard deviation of pain scores in full—a parameter that is essential for sample size calculations. To date, we have not found any publications comparing diclofenac gel directly with topical piroxicam, with standard deviations appropriate for use in statistical calculations. So, even though the comparator was capsaicin, this reference was chosen because it is quite representative in terms of pain type and study design.

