7.4.2 Statistical Analysis Plan

The statistical analysis will be performed after data finalization and database lock, following the predefined analysis sets (PPS, FAS, and Safety Analysis Set). All analyses will be conducted using standard statistical software (e.g., SPSS, SAS, or R), with the level of statistical significance set at $p < 0.05$, unless otherwise adjusted.

Efficacy Analysis

- **Primary Endpoint (Pain Score using Brief Pain Inventory):**
 - **Test: Analysis of Covariance (ANCOVA)** adjusting for baseline BPI score

- **Equivalence testing:** Pairwise comparisons using **two one-sided t-tests (TOST)** to assess whether the difference in mean change from baseline falls within the equivalence margin (± 1.0)
- **Assumptions:** Normality and homogeneity of variance will be checked. If violated, non-parametric equivalent (e.g., **Wilcoxon rank-sum test**) will be used.
- **Secondary Endpoints:**
 - **Range of Motion (ROM) and Muscle Strength:**
 - **Test:** Repeated Measures ANOVA or mixed-effects model, depending on data completeness and correlation structure
 - If non-normal: **Friedman test** or **Wilcoxon signed-rank test** for within-group, **Kruskal-Wallis test** for between-group comparisons.
 - **Thermal Sensation, Comfort, and Acceptance (ASHRAE Scale):**
 - **Test:** Chi-square test or Fisher's exact test for categorical comparisons
 - **Ordinal regression** may be used to explore patterns of thermal perception across groups.
 - **Responding Analysis (pain reduction ≥ 3 points):**
 - **Test:** Chi-square test for group-wise comparison of response rates
 - **Risk difference** and **number needed to treat (NNT)** will be calculated.

Safety Analysis

- **Adverse Events (AEs) and Adverse Drug Reactions (ADRs):**
 - **Test:** Chi-square test or Fisher's exact test for comparing incidence across groups
 - Descriptive statistics for type, severity, onset, and duration
 - **Severity grading** and **causality assessment** using **Naranjo's algorithm**.
- **Rescue Medication Use:**
 - **Test:** Poisson regression or negative binomial regression if data are overdispersed
 - Summarized as a mean number of doses used per participant and compared between groups.

Demographic and Baseline Characteristics

- **Continuous Variables** (e.g., age, BMI):
 - **Test:** One-way ANOVA or **Kruskal-Wallis test** (if non-normal distribution)
- **Categorical Variables** (e.g., sex, diagnosis):
 - **Test:** Chi-square test or Fisher's exact test as appropriate

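### The objective claims equivalent safety, but the protocol sets an equivalence criterion only for the pain score

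*Protocol*

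**What the plan says.** Section 4 sets one objective for the three gels: "The objectives of this study is to demonstrate the equivalency of efficacy and safety in reducing musculoskeletal pain". Section 5 calls the trial a Phase 3 confirmatory study. Section 5.2 makes safety the first secondary endpoint: "the number of participants who experienced adverse events (including serious adverse events) with each symptom present will be recorded", with causality assessed by Naranjo's algorithm.

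Section 7.4.2 runs its analyses "with the level of statistical significance set at" p < 0.05 unless adjusted, and treats the two parts of the objective differently:

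- **Pain score:** ANCOVA, plus pairwise two one-sided t-tests "to assess whether the difference in mean change from baseline falls within the equivalence margin" of ±1.0.
- **Adverse events and adverse drug reactions:** "Chi-square test or Fisher's exact test for comparing incidence across groups", with descriptive summaries and causality grading.
- **Rescue medication, also listed under safety:** "Poisson regression or negative binomial regression if data are overdispersed", comparing mean doses per participant between groups.

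Section 6.7 sizes the trial on the pain score (SD 1.81, margin 1.0) and arrives at 60 participants per arm, 180 in total.

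**The concern.** An equivalence claim needs a margin and a rule for when the data exclude differences beyond it. The protocol supplies both for pain and neither for safety. Failing to reject no difference in AE incidence does not show that the incidences are close. The objective therefore names a property that the stated safety analysis has no means of establishing.

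This is more than detail left to a separate analysis plan. The protocol itself states the objective and itself fixes the safety tests, and the two do not fit.

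The wording has consequences. The test gel adds methyl salicylate, menthol and eugenol to piroxicam, so a difference in skin tolerability is a fair question. Section 2.2 intends the result to feed treatment guidance, and Section 7.19 lets the sponsor use it in applications for marketing approval.

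**Working it through.** **1. The plan's own figure.** Section 6.7 prints "n = ((2.39 + 0.84) \times 1.81 / 1.0)^2". With those inputs, 2.39 + 0.84 = 3.23; 3.23 × 1.81 = 5.846; 5.846² = 34.2. The stated 54 comes from writing 4.059 in place of 3.23: (4.059 × 1.81)² = 54.0. The dropout step is right: 162 / 0.90 = 180. The arithmetic slip is a separate matter. What counts here is that the only inputs are a pain SD and a pain margin. No AE rate, AE margin or safety power enters.

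**2. Inputs for the safety check.** From the protocol: 60 per arm, three equal arms, p < 0.05. Assumed, because the protocol states none: AE rates of 2% to 20% and, for step 5, a 10-point margin.

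**3. One possible result: 3/60 against 9/60.**
- Uncorrected chi-square: pooled rate 12/120 = 0.10; standard error √(2 × 0.10 × 0.90 / 60) = 0.0548; z = 0.10 / 0.0548 = 1.83; p = 0.068. Fisher gives p = 0.125.
- Risk difference 10 points; standard error √(0.05 × 0.95/60 + 0.15 × 0.85/60) = 0.0540; 95% CI 10 ± 1.96 × 5.40, that is −0.6 to 20.6 points.
- Three arms with 3, 3 and 9 events: expected 5 each; chi-square = (4 + 4 + 16) / (60 × 0.0833 × 0.9167) = 5.24 on 2 degrees of freedom; p = 0.073.

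A threefold difference in observed rates is thus non-significant by all three tests.

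**4. How often the test is non-significant when rates truly differ.** For two arms, binomial probabilities are summed over all pairs of counts with p ≥ 0.05. For three arms, 200,000 trials are simulated with the third arm at the lower rate.

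| Assumed true rates | Two-arm chi-square, uncorrected | Two-arm Fisher | Three-arm chi-square |
|---|---|---|---|
| 5% vs 10% | 83% | 91% | 82% |
| 5% vs 15% | 54% | 67% | 50% |
| 10% vs 20% | 67% | 75% | 64% |

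**5. What 60 per arm could show if a margin existed.** True difference 0, common rate p, margin m = 10 points, SE = √(2p(1−p)/60):
- half-width of the 95% CI = 1.96 × SE;
- TOST power = 2Φ(m/SE − z) − 1, taken as 0 if negative;
- n per arm for 80% power = 2p(1−p)(z + 1.282)²/m².

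Here z = 1.645 at one-sided alpha 0.05, and 2.128 at 0.0167, the Bonferroni level of Section 6.7.

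| AE rate | 95% half-width | Power at 60 per arm (0.05 / 0.0167) | n per arm for 80% (0.05 / 0.0167) |
|---|---|---|---|
| 2% | 5.0 points | 98% / 93% | 34 / 46 |
| 5% | 7.8 points | 62% / 30% | 82 / 111 |
| 10% | 10.7 points | 14% / 0% | 155 / 210 |

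Whether 60 per arm is enough thus depends on a rate and a margin that the protocol does not state.

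**The case against.** The best reply is that equivalence was only ever meant for efficacy. The justification in Section 4 itself speaks only of the same efficacy. Section 2.2 speaks of comparing effectiveness, Section 5 of comparing efficacy and safety, and Section 5.2 makes safety secondary. On that reading the conflict comes down to two words in one sentence. This largely stands: it lowers the severity and points to a wording repair. It does not remove the conflict, because Section 4 is the statement of objectives.

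A reader might infer that the protocol plans to declare safety equivalent when p exceeds 0.05. It says no such thing; it calls the test a comparison of incidence and adds descriptive summaries. What can be said is that no criterion connects the safety analysis to the safety objective.

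A reader might also infer that 60 per arm is too few. The documents do not support that either: at a 2% rate and a 10-point margin, 60 would suffice. The background does suggest low rates, with no adverse experiences in 20 healthy volunteers on piroxicam gel (Section 2.1) and topical NSAID events similar to placebo (Section 2.2). That leaves the rate open, however. Zero events in 20 is compatible with a true rate up to 1 − 0.05^(1/20) = 13.9% (one-sided 95% bound), and those volunteers did not use the combination.

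Finally, the two-arm figures are not exactly the planned test, which compares incidence across three groups. The three-arm figures are close and lead to the same conclusion.

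**Conclusion.** The point holds in a limited form. The protocol sets out to demonstrate equivalent safety, yet neither the AE comparison nor the rescue-use comparison has a margin or an equivalence criterion, so the stated analysis cannot deliver that part of the objective. The obstacle is the missing criterion, not the sample size as such.

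A non-significant AE test would say little: under assumed rates of 5% and 15% it occurs in about half to two thirds of trials, depending on the test, and the interval for a difference spans roughly ±8 to ±11 points at rates of 5% to 10%. All of these figures rest on assumed AE rates.

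It would go too far to say that the trial's main conclusion is undermined. The primary endpoint and its equivalence test do not depend on the safety wording. This should be fixed before results are known, but it is not a fatal defect.

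**What to change.** In Section 4, limit equivalency to efficacy and restate the safety aim as to describe and compare. In Section 7.4.2, report for each test-versus-comparator pair the risk difference in AE incidence with its 95% confidence interval; the section already plans risk differences for the pain responder analysis. Add a sentence that a non-significant AE test will not be reported as equivalent safety.

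The cost is a few lines of text and two intervals, with no extra participants or data. The downside is a weaker safety claim.

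If the sponsor does want to claim equivalent safety, the alternative is a justified AE margin, a confidence-interval or TOST rule, and a sample size to match. The second table under the working shows how strongly that size would depend on the assumed rate.
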